14.9 Missing Data

A tipping point sensitivity analysis will be conducted in which missing values in each group are separately assumed to be either successes or failures. Treatment group differences will be computed based on all possible combinations of assigning success or

failure to the primary overall success endpoint to the subjects in the two groups. For example, one scenario will be that all missing S+A device observations are failures and all missing AA observations are successes. The next scenario would have one success and the remaining missing values as failure for S+A and all missing AA controls as successes. For each scenario, the one-sided normal approximation p-value will be determined. These results will be plotted using a dot plot with the number of missings assumed as failures for S+A on the x-axis and the number of missing assumed as failures for AA controls on the Y-axis. The dots will be color coded to indicate whether or not the primary statistical conclusion changes under each individual scenario. If the fraction of scenarios in which the statistical conclusion changes is small, the primary results will have been shown to be robust against assumptions concerning missingness. Therefore, the primary hypothesis test will be conducted using the mITT analysis set in conjunction with the tipping point sensitivity analysis to account for mITT subjects who are not evaluable for primary CCS (either at 12 months or 24 months). If the fraction of missing data is larger than 10%, then multiple imputation (MI) will be performed in order to provide a comparison that includes all mITT subjects in order to further assess the potential impact of missing data. The MI will be implemented using SAS Proc MI and MIANALYZE and based on a monotonic missing value pattern.

14.10 Poolability, Stratified Analyses, and Covariates

Site poolability will be evaluated using a random effects meta-analysis approach using the R package metafor to implement the analysis. True effects are assumed to be normally distributed with mean μ and variance τ^2 .

By imposing a specified distribution on the site-to-site variability, i.e. a normal distribution with mean μ and variance τ^2 , sensitivity to small sample sizes in individual sites is reduced and the parameters reflecting the magnitude of site-to-site variability are naturally derived. The quantitative measure of the magnitude of heterogeneity is I^2 . I^2 is the fraction of τ^2 that is due to effect size heterogeneity, as opposed to sampling variance. Fractions 25% and less are considered small. If there is significant site to site variability, the impact on this variability will be evaluated using a random effects logistic regression.

Primary endpoints and selected secondary endpoints will be subjected to stratified analyses in order to evaluate poolability and heterogeneity of device group differences. Stratifications will include age (<55 vs ≥ 55 years), gender, body mass index (<30 vs ≥ 30 kg/m²), femoral vs tibial primary lesion, and unipolar vs bipolar lesion polarity status.

Analyses will focus on determining if clinically significant group differences exist for variables that potentially have important associations with clinical outcomes.

Identification of such variables will be based on clinical significance and not statistical significance since the study was not powered to detect any specific magnitude of difference between randomized groups. Nonetheless, conventional p-values for baseline group differences will be provided for descriptive purposes only and as a visual aid in identifying covariates worthy of further consideration. Variables for which clinically significant group differences are observed that are also associated with outcomes will be utilized as covariates in supporting analyses design to characterize how relative efficacy may vary

across subgroups. Additionally, using data from the investigational device only, a failure risk analysis will be performed starting with the same set of baseline covariates with the possible addition of procedure and device specific variables.

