8.0 Subject Selection Criteria

8.1 Inclusion Criteria

Candidates must meet ALL of the following:

- 1) Voluntary signature of the IRB/REB approved Informed Consent,
- 2) Male or female subjects between the ages of 30 to 75 years,
- 3) Body Mass Index ≤ 40 (BMI=kg/m²),
- 4) Has experienced pain in study knee for at least 3 months,
- 5) Kellgren-Lawrence grade 1-3 Osteoarthritis in the study knee, as reviewed on preoperative XR imaging,
- 6) BML is confirmed on T2 weighted or Proton Density MR Imaging by presence of white signal,
- 7) Single BML of tibia, single BML of femur, or adjoining BMLs of tibia & femur, in the same compartment, extending to the articular surface of the joint,
- 8) Surgical candidate for knee arthroscopy due to mechanical symptoms, meniscus tear, loose body and/or synovitis,
- 9) Must record a response, at the preoperative study visit, of moderate to extreme pain for any one of the KOOS Pain Scale questions, P2 through P9,
- 10) Index knee alignment is defined radiographically as one of the following: Neutral, \leq to 6° mechanical varus, or \leq 6° mechanical valgus,
- 11) Ligaments in the study knee are stable,
- 12) The contralateral (non-study) knee is stable and functional,
- 13) Is refractory to conservative non-surgical management
 - a) having failed 2 or more of the following: hyaluronic acid injection, corticosteroid injection, NSAIDs, physical therapy, bracing, activity modification, or minimal surgical intervention (e.g., arthroscopy, debridement/chondroplasty, and/or loose body removal)
 - b) and is ≥ 3 months from the start of treatment (these treatments can continue up to the time of the randomized procedure; injections to be completed per Section 10.4.7),
- 14) Must be physically and mentally willing and able, in the Investigator's opinion at the time of enrollment, to be compliant with the protocol, including all follow-up visits, survey completion, weight-bearing restrictions, and post-operative rehabilitation.

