14.5 Sample Size Determination

For testing the primary superiority hypothesis as defined above and assuming true CCS rates of 0.80 and 0.60 for S+A and AA, respectively, a total of 174 subjects (116 and 58, respectively) are need for 80% power. This value is increased by 15% to 201 to account for losses-to-follow-up (134 S+A and 67 AA).

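### The planned heterogeneity analyses for age and BMI are two-way splits at 55 years and 30 kg/m²; if the device effect changes roughly linearly with either variable, the split discards about a quarter to nearly a half of the information on that gradient

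*Combined protocol and SAP*

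**What the plan says.** Section 14.10 states the purpose of the subgroup work: the endpoints "will be subjected to stratified analyses in order to evaluate poolability and heterogeneity of device group differences. Stratifications will include age" and four other factors. With the cut-points, the list runs: "Stratifications will include age (<55 vs ≥ 55 years), gender, body mass index (<30 vs ≥ 30 kg/m²"), femoral versus tibial primary lesion, and unipolar versus bipolar status. No reason is given for either cut-point.

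Two other routes appear in the same section. Variables that show clinically significant baseline differences between groups, and are also associated with outcome, will be "utilized as covariates in supporting analyses design to characterize how relative efficacy may vary" across subgroups; the form in which a covariate enters is not stated. A failure risk analysis is planned in the investigational arm alone.

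Section 8.1 admits "Male or female subjects between the ages of 30 to 75 years" and BMI up to 40 kg/m². Section 14.5 sizes the trial by "assuming true CCS rates of 0.80 and 0.60 for S+A and AA", giving 116 and 58 evaluable subjects. The documents give no mean, SD or expected share above 55 years or above 30 kg/m².

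**The concern.** Gender, lesion site and polarity are naturally categorical; age and BMI are not. Eligibility already requires both to be known as numbers. The split treats ages 54 and 56 as different and ages 56 and 75 as the same. If the device effect drifts with age or BMI, comparing two broad strata is a less precise way to see it than a treatment-by-covariate term, and the answer depends on where the cut falls.

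The other two routes do not fill the gap. In a randomised trial a baseline imbalance in age arises by chance and says nothing about whether age modifies the effect, so a balanced age would never be examined that way. The single-arm failure analysis cannot estimate how a difference between arms varies.

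At stake is the precision of an exploratory assessment that is already weak at the planned size. Sections 3.0 and 7.0 report that enrollment stopped early, so it may be weaker still.

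**Working it through.** **1. The plan's own figure.** Inputs from Sections 14.2 and 14.5: CCS 0.80 versus 0.60, 2:1 allocation, one-sided alpha 0.04 (month 24), 80% power. The pooled-variance normal formula with control-arm size n, ratio r = 2 and d = 0.20 is

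n = [z(0.96)·√((r+1)·p̄·q̄) + z(0.80)·√(r·0.24 + 0.16)]² / (r·d²), with p̄ = (0.60 + 2 × 0.80)/3 = 0.733.

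This gives 51 controls (153 in total). With the continuity correction it gives 58, so 58 + 116 = 174, matching the plan. Then 174 × 1.15 = 200.1, taken to 201 to keep 2:1. This figure concerns the primary test; the plan states no figure for heterogeneity by age or BMI.

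**2. Information kept by a split.** For an effect that changes linearly with covariate X, the share of information kept when X is replaced by its above/below indicator is the squared correlation between the two.

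- Normal X with a proportion p on one side and cut at z: kept = φ(z)² / [p(1−p)].
- Uniform X: kept = 3p(1−p).

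| Assumed distribution | Kept | Lost |
|---|---|---|
| Normal, 50/50 | 63.7% | 36.3% |
| Normal, 40/60 | 62.2% | 37.8% |
| Normal, 35/65 | 60.3% | 39.7% |
| Normal, 30/70 | 57.6% | 42.4% |
| Uniform age 30-75, cut 55 (p = 25/45) | 74.1% | 25.9% |
| Uniform BMI 20-40, cut 30 (p = 0.5) | 75.0% | 25.0% |
| Truncated normal age, mean 50-60, SD 8-12, limits 30-75 | 56-68% | 32-44% |
| Truncated normal BMI, mean 27-33, SD 4-6, limits 17-40 | 53-68% | 32-47% |

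The eligibility limits are from Section 8.1. The means, SDs and lower BMI limits are assumptions. Over this grid the loss runs from about 25% to 47%. In the normal rows, the split needs 1/0.637 = 1.57 to 1/0.576 = 1.74 times as many subjects for the same precision.

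**3. Effect on power.** Take a linear interaction detectable with 80% power on the continuous scale at two-sided 0.05. Its noncentrality is 1.960 + 0.842 = 2.802.

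- 50/50: 2.802 × √0.637 = 2.236; Φ(2.236 − 1.960) = 61%.
- 30/70: 2.802 × √0.576 = 2.127; Φ(2.127 − 1.960) = 57%.

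Starting from 50% power, the corresponding figures are 35% and 32%.

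**4. Power this trial would have.** Logistic models with a treatment-by-age term were simulated at 116/58 with rates 0.80/0.60, an assumed age mean of 57 and SD of 9, and two-sided 0.05. Ranges span separate runs.

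| Interaction, log-odds per SD | Continuous | Split |
|---|---|---|
| 0 | about 5% | about 5% |
| 0.2 | 9% | 7% |
| 0.3 | 13% | 10% |
| 0.5 | 24-25% | 17% |
| 0.8 | 53-57% | 39-40% |
| 1.0 | 72-75% | 52-54% |

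For scale, the design rates imply a treatment log-odds ratio of ln 4 − ln 1.5 = 1.386 − 0.405 = 0.98. An interaction of 1.0 per SD would therefore remove the whole benefit one SD from the mean, so the last two rows are large gradients.

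With an illustrative 80/40, since the enrolled number is not given, 0.5 per SD is detected in 21% versus 15% of trials.

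**The case against.** The strongest reply is that the change would seldom alter a conclusion. For gradients up to about 0.5 log-odds per SD, both methods miss the interaction in most trials. This stands, and it rules out an inference a reader might draw: that splitting makes a real gradient likely to be reported as poolable. Low power for modest gradients belongs to the sample size under either method. For age and BMI, Section 14.10 also sets no interaction test, significance level or rule for declaring poolability; its 25% I² benchmark concerns sites. The 0.05 test above is a yardstick supplied for this check.

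Second, linearity is an assumption. If the effect were a step exactly at 55 years or 30 kg/m², the split would lose nothing and the linear term would be the inefficient choice. The plan makes no such argument for its cut-points.

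Third, the cuts are prespecified, which prevents data-driven choices, and the tables are easy to read. That is a good reason to keep them, but not to rely on them alone.

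Fourth, one might read Section 14.10 as examining age and BMI through splits and nothing else. That is slightly too strong, because the supporting covariate analyses could include them in some form. That route is conditional and unspecified, so it does not replace a planned interaction analysis.

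**Conclusion.** The point holds as a low-cost improvement. The specified heterogeneity analyses for age and BMI are two-way splits, with no planned analysis that keeps the recorded values. Under a roughly linear gradient, the loss is about 25-47% of the information across the assumed distributions. A reader might take 36-42% as the loss in this trial, but the documents do not support that: it needs a normal covariate, a linear modifier and splits between 50/50 and 30/70, none of which they give.

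Nor does the point reach the main result. The primary CCS test, the 0.01/0.04 alpha division and the sample size do not depend on these analyses, which are exploratory.

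**What to change.** In Section 14.10, add treatment-by-age and treatment-by-BMI terms with the recorded values kept continuous, either linear or as a spline to relax linearity. Report the estimated treatment effect with confidence intervals at several values, for example ages 45, 55 and 65 and BMI 25, 30 and 35, and base the description of heterogeneity on those estimates. Keep the <55/≥55 and <30/≥30 tables for display. Label the analysis exploratory and, if the plan is not amended, note the addition in the final report as Section 14.11 requires.

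The cost is SAP wording and two model terms, with no new data. The downside is a linearity assumption, or a few extra degrees of freedom if a spline is used. Intervals will be wide at this sample size.

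### Section 14.10 uses chance baseline imbalance to choose which further variables enter the analyses of how efficacy varies, and names no treatment-by-variable interaction

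*Combined protocol and SAP*

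**What the plan says.** Section 14.10 of the combined protocol and SAP has three parts that bear on this point.

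- **Stratified analyses.** "Primary endpoints and selected secondary endpoints will be subjected to stratified analyses in order to evaluate poolability and heterogeneity of device group differences". The listed factors are age (cut at 55 years), gender, BMI (cut at 30), "femoral vs tibial primary lesion, and unipolar vs bipolar lesion polarity status". These analyses do not depend on any observed imbalance.
- **Covariate rule.** "Variables for which clinically significant group differences are observed that are also associated with outcomes will be utilized as covariates in supporting analyses design". The sentence gives the aim of these analyses as "to characterize how relative efficacy may vary" from one subgroup to another. The surrounding sentences show that the group differences meant are baseline differences between the randomised arms: "conventional p-values for baseline group differences will be provided for descriptive purposes only and as a visual aid in identifying covariates worthy of further consideration". On the threshold, the plan says only this: "Identification of such variables will be based on clinical significance and not statistical significance". It gives no numeric threshold, no list of candidate variables and no model form.
- **Failure risk analysis.** "using data from the investigational device only, a failure risk analysis will be performed starting with the same set of baseline covariates", with procedure and device variables possibly added.

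Assignment is randomised 2:1 within site and polarity (Section 7.0).

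**The concern.** The covariate rule joins a purpose to a selection criterion that belongs to a different purpose. Whether relative efficacy varies across subgroups is a question of effect modification. The rule admits a variable only if the arms differ on it at baseline and it is associated with outcome. Under randomisation the first condition is met by chance. The second identifies prognostic factors. Neither involves a difference in treatment effect between levels of the variable.

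A baseline imbalance in a prognostic variable is a reason to report an adjusted treatment effect. It is not a reason to expect that the effect differs between subgroups. Screening on clinical rather than statistical significance does not help, because the quantity being screened is still chance imbalance.

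A modifier outside the five stratifiers may therefore go unexamined because the arms happened to be balanced on it, while a variable that modifies nothing may be examined because they were not. Which variables are looked at would also rest on an unstated judgement made after the data are seen.

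**Working it through.** **Inputs.** Planned arms are 134 S+A and 67 AA; evaluable arms are 116 and 58 (Section 14.5). Section 14.10 gives no figure for the covariate rule, so the imbalance thresholds below are assumptions.

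**The plan's own sample size.** With AA 0.60, S+A 0.80, 2:1 allocation, one-sided alpha 0.04 and 80% power, the pooled rate is (0.60 + 2 × 0.80)/3 = 0.733. The uncorrected AA size is [1.751 × √(1.5 × 0.733 × 0.267) + 0.842 × √(0.24 + 0.16/2)]² / 0.20² = 50.7. The continuity correction multiplies this by ¼ × [1 + √(1 + 6/(2 × 50.7 × 0.20))]², giving 58. So 58 + 116 = 174, as stated, and 174 × 1.15 = 200.1, stated as 201.

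**Chance of passing the imbalance screen.** For a standardised difference d, the chance is 2 × [1 − Φ(d/SE)] with SE = √(1/n₁ + 1/n₂). SE is √(1/134 + 1/67) = 0.150 at 134:67 and √(1/116 + 1/58) = 0.161 at 116:58.

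| Assumed threshold d | 134:67 | 116:58 |
|---|---|---|
| 0.10 | 50% | 53% |
| 0.20 | 18% | 21% |
| 0.25 | 10% | 12% |
| 0.30 | 4.5% | 6% |

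For a binary variable at 50% prevalence, d = 0.20 is a 10-point gap. Simulation of that case gave 18% at 134:67 and 22% at 116:58. None of these chances depends on whether the variable modifies the effect. They cover only the imbalance half of the rule; also requiring an association with outcome can only lower them.

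**Smaller trial.** Enrolment stopped early and the achieved size is not given. At an assumed 80:40, SE = √(1/80 + 1/40) = 0.194, and the chances rise to 61%, 30% and 20% at 0.10, 0.20 and 0.25. For a 50% binary variable, simulation gave about 65%, 34% and 22%; the excess comes from discreteness.

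**Illustration of the cost.** Assume that an interaction is tested (two-sided 0.05, risk-difference scale) once a variable passes. Take a binary modifier at 50% prevalence, 134:67, so the cells hold 67 per level in S+A and 33.5 in AA.

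- *30-point interaction* (S+A 0.95 vs 0.65; AA 0.60 at both levels). Variance = (0.0475 + 0.2275)/67 + 0.48/33.5 = 0.0184, SE = 0.136, power = Φ(0.30/0.136 − 1.96) ≈ 60%. With a 10-point imbalance required first: 0.60 × 0.18 ≈ 11%. Simulation gave 60% and 11%.
- *20-point interaction with high control success* (S+A 0.90 vs 0.70; AA 0.80). Variance = (0.09 + 0.21)/67 + 0.32/33.5 = 0.0140, SE = 0.118, power = Φ(0.20/0.118 − 1.96) ≈ 40%. Screened: 0.40 × 0.18 ≈ 7%.

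If a variable were instead entered only as a main effect, the model would give one adjusted treatment effect and would not assess variation at all.

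**The case against.** The strongest reply is that 14.10 already has a heterogeneity analysis. The stratified analyses cover five clinically sensible factors whatever the balance, and the list is introduced in a way that does not close it. A reader might infer from the covariate rule that true effect modifiers will usually never be examined. The documents do not support that: the five stratifiers are always examined, and for other variables the answer turns on a threshold the plan does not state. At 0.10, about half would pass.

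A reader might also infer that the covariate models contain main effects only. The text does not say so. Interaction terms are left unspecified, not excluded.

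Nor should the failure risk analysis be faulted for failing to detect modification. It is presented as a risk analysis in the device arm and claims no such aim. The limit is on interpretation: without control data, it cannot separate a factor that predicts failure in both arms from one that changes the benefit.

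Three further points stand. Interaction tests in a trial of this size are weak in any case: in the 20-point example the direct test itself misses about 60% of the time. Eight interactions read at 0.05, if independent, carry a 1 − 0.95⁸ ≈ 34% chance of at least one false positive. And nothing in the documents makes the question of who benefits a main objective after enrolment stopped; Section 7.0 justifies continued follow-up by revisions, reoperations, adverse events, KOOS and numeric pain.

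What the reply does not answer is the mismatch itself. For any variable outside the five, entry depends on chance imbalance, which carries no information about the stated question.

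**Conclusion.** The point holds within a limited scope. In 14.10 a criterion suited to covariate adjustment is used to choose variables for describing variation in efficacy, and no treatment-by-variable interaction is named. It affects baseline variables outside the five stratifiers, for example baseline KOOS Pain, Kellgren-Lawrence grade and alignment.

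At the planned size, whether such a variable is examined is close to a coin toss under a loose threshold and about a one-in-five to one-in-ten event under a moderate one. These figures rest on assumed thresholds, on planned rather than achieved numbers, and on treating allocation as simple randomisation for these variables. No single figure for lost power can be attached to the trial, since that also depends on an assumed interaction and control rate. The analyses are supporting ones and the primary conclusion is untouched, so this should be corrected but is not critical.

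**What to change.** In 14.10, for analyses of variation in efficacy, remove the condition that the arms differ at baseline, and remove the use of baseline p-values to identify covariates. Replace them with text to this effect:

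> Variation in relative efficacy will be assessed for a fixed list of baseline variables: the five stratification factors plus baseline KOOS Pain, Kellgren-Lawrence grade and knee alignment. Each will be assessed regardless of baseline balance, by a treatment-by-variable interaction in a CCS model using both arms. The interaction estimate will be reported with its 95% confidence interval and labelled exploratory.

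The three added variables are examples; the sponsor may prefer another short list, provided that it is named and fixed. All three are already collected: KOOS at the preoperative visit (Section 9.3 and Table 1), and Kellgren-Lawrence grade and alignment as fields on the eligibility form (Section 21.0, revision 3.0).

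Baseline imbalance may still guide covariate-adjusted sensitivity analyses, described as such. The S+A-only failure risk model may stay if it is labelled prognostic and not read as evidence of effect modification.

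The cost is a change of SAP wording and a few extra model runs. The downside is a set of imprecise exploratory interactions without multiplicity control, which is why estimates and intervals should be reported rather than significance claims. Because enrolment stopped after an interim analysis, the report should also state when the list was fixed. The primary test, alpha and data collection do not change.
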